## 1.0 PROTOCOL SUMMARY AND/OR SCHEMA

Title: An exploratory study to evaluate the mediators of sensitivity and resistance to nivolumab plus ipilimumab in patients with advanced NSCLC

Study Design: This is an open-label, single-center, single-arm, phase II exploratory study of nivolumab 3mg/kg q 2 weeks in combination with ipilimumab 1mg/kg q 6 weeks. The target population includes patients with advanced stage NSCLCs. This study aims to examine the factors that may contribute to sensitivity or resistance to nivolumab plus ipilimumab in patients with advanced NSCLCs. There are several objectives to this study, which are structured around a model of T-cell recognition of cancer.

Eligible patients must have at least one site of disease that is amenable to standard-of-care surgical resection or a core needle biopsy. For those undergoing standard of care resection, residual measurable disease following resection is required.

Eligible patients must have had no more than 2 prior regimens of chemotherapy and no prior immunotherapy. Patients with *EGFR* mutations or *ALK* re-arrangements must have had prior tyrosine kinase inhibitors. Those with auto-immune disease, concurrent treatment with alternative anti-cancer therapy or systemic immunosuppressants, or untreated brain metastases are excluded from study.

Patients will have a pre-treatment, standard-of-care tumor resection or tumor biopsy for fresh tissue collection. Patients will then start nivolumab 3mg/kg day 1 and continue this every 2 weeks during the study protocol. Patient will concurrently start ipilimumab 1mg/kg day 1 and continue this every 6 weeks during the study protocol. Tissue collection and correlative studies planned described below.

	Pre-Rx	C1D1	C2D1	C2D8	C3D1	C4D1 and each cycle thereafter
Nivolumab 3mg/kg		X	X		X	X
Ipilimumab 1 mg/kg		X				X and every 6 weeks thereafter
Biospecimen collection for analysis						
Tumor resection or biopsy	X					
Tumor biopsy				X		
Isolation of TILs	X					
PBMCs	X	X	X	X	X	X and every 6 weeks thereafter
Tumor-based analysis						

Mutation burden	X					
Candidate neoantigens	X					
Co-stimulatory receptors and ligands	X			X		X and every 6 weeks thereafter
T cell analysis (TILs and/or PBLs)						
Identification of antigen-specific T-cells	X	X		X		X and every 6 weeks thereafter

Project	Methods
Mutation burden	Whole exome / transcriptome
Candidate neoantigens	Bioinformatics
Co-stim receptors and ligands	IHC
Antigen specific T-cells	MHC-multimer assays ICS assays

## 2.1 OBJECTIVES AND SCIENTIFIC AIMS

Nivolumab produces a response in ~15-20% in patients with advanced NSCLC and the combination of PD-1 blockade plus CTLA-4 blockade appears to have a response rate of ~30%(1). We have recently demonstrated that somatic mutation burden is associated with response to PD-1 blockade monotherapy in a retrospective study (2), but the predictors and mediators of response to nivolumab in combination with ipilimumab are not known. In this prospective study, we aim to examine mechanisms of sensitivity and resistance to nivolumab plus ipilimumab by dissecting the individual components that contribute to T-cell recognition of and response to a cancer cell.

A cornerstone of cancer immunotherapy is the ability of the adaptive immune system to recognize a cancer as foreign, i.e. non-self. One way that a cancer can appear foreign is by the accumulation of somatic mutations. Some of these mutations are oncogenic, while others are passengers. But irrespective of their oncogenic potential, each of these mutations has the potential to contribute to the immunogenicity of a cancer. The primary objective of this study is to explore how these somatic mutations in cancer mediate response or resistance to nivolumab plus ipilimumab. To fully contextualize the T-cell response to cancer, we will evaluate in parallel the other factors involved in T-cell and cancer cell interactions, including expression of co-stimulatory ligands on tumor cells and in the tumor microenvironment and expression of exhaustion/activation receptor on T-cells.

Primary objectives:

- 1) Explore the relationship between mutational burden and response to nivolumab plus ipilimumab therapy
- 2) Identify candidate neoantigens and explore their associations with response to nivolumab plus ipilimumab therapy

- 3) Identify neoantigen-specific T-cells using technology such as *in vitro* using MHC-multimer or intracellular cytokine staining.

#### Secondary objectives

- 1) Examine MHC and co-stimulatory receptor and ligand expression in tumor-microenvironment and explore their relationship with response to nivolumab plus ipilimumab.

### 3.0 BACKGROUND AND RATIONALE

#### INTRODUCTION TO LUNG CANCERS

Lung cancer is the most common cancer and leading cause of cancer related death worldwide, accounting for more than 1.6 million cases and 1.3 million deaths annually (3). For patients with advanced stage non-small cell lung cancer (NSCLCs), the most common form of lung cancer in the United States, cytotoxic chemotherapy improves outcomes (4, 5) but durable disease control is disappointingly rare – fewer than 5% of patients are alive 5 years later and median survival is ~10 months (6, 7). Histology-specific chemotherapy (8), maintenance chemotherapy (9-13), the addition of bevacizumab (14), and the identification of targetable driver oncogenes (15-20) have all improved outcomes, but there remains an urgent need for better treatment strategies for the majority of patients with advanced NSCLCs. T-cell checkpoint inhibitors, particularly those targeting PD1 and PDL1, have recently demonstrated promising activity in NSCLCs and represent a new paradigm for considering the treatment of patients with lung cancers.

#### T-CELL CHECKPOINT INHIBITION IN NSCLCs

T-cell checkpoint inhibitors targeting CTLA-4 (ipilimumab (21)), PD-1 (nivolumab, and other similar therapies in development (22-25)) and PDL1 (26, 27) have demonstrated effectiveness in advanced NSCLCs and validated the importance of cancer immunotherapy in the treatment of patients with NSCLCs.

#### **PD-1 AND PD-L1**

Programmed Cell Death-1 (PD-1; CD279) is a cell surface receptor on T-cells that is induced after T-cell activation. When PD-1 engages with its cognate ligands (PDL1, also known as B7-H1, or PD-L2, also known as B7-DC), it signals intracellularly in T-cells to inhibit effector T-cell function (28) via induction of effector T-cell apoptosis, suppression of effector T-cell proliferation or cytokine production (29-32). PDL1 and PD-L2, ligands of PD-1, are expressed not only by APCs but also by tumor cells and cells in the tumor microenvironment. An overexpression of PD-1 ligands by tumor cells and cells in its microenvironment leading to ineffective tumor infiltrating effector T-cells is postulated to be one important mechanism by which tumor cells prevent immune-mediated destruction (28, 33). Indeed, overexpression of the PD-L1 within solid tumors has been associated with poor prognosis and diminished tumor infiltrating effector T-cells (34-36), including NSCLCs (37, 38).

Aimed at reversing the immune inhibitory signals to restore effective tumor directed immune attack, multiple anti-PD-1 and anti-PDL1 monoclonal antibodies (mAb) are currently in development.

## **Nivolumab**

Nivolumab (BMS-936558) is a fully human, IgG4 (kappa) isotype mAb that binds PD-1 on activated immune cells and disrupts engagement of the receptor with its ligands (PD-L1 and PD-L2), thereby abrogating inhibitory signals and augmenting the host antitumor response. In an early clinical trial, nivolumab demonstrated activity in several tumor types, including melanoma, renal cell cancer (RCC), and NSCLCs (22). Treatment was well tolerated, no dose-limiting toxicities were observed, three objective responses, including one complete response, were reported.

A second phase I study of 296 patients with advanced solid tumors treated with nivolumab given every two weeks in escalating dose cohorts has also been reported (24). 122 patients had NSCLCs. 55% had been treated with  $\geq 3$  prior regimens. Only 8% of those with NSCLCs experienced treatment related grade 3-4 toxicity (fatigue, pneumonitis, transaminitis being most common), although two patients with NSCLCs died of treatment-related pneumonitis. Of all NSCLC patients evaluable for clinical activity [i.e. all doses], 17% has an objective response; in those who received 3 or 10mg/kg (the recommended phase II doses), the response rate was 22% (21/96). Impressively, the 24-week PFS rate among all NSCLCs patients treated at 3mg/kg was 42-45% (23, 39). These results are similar to the ORR and median PFS from achieved with first-line platinum-based chemotherapy (ORR ~30%, median PFS ~5 months (8, 14)) and appear numerically superior to standard second-line treatment options (including erlotinib, docetaxel, or pemetrexed; ORR 3-8%, median PFS 6-8 weeks (40, 41)).

Since then, nivolumab has since been studied in several studies include two phase 3 studies of nivolumab versus docetaxel in patients with advanced NSCLCs previously treated with one line of therapy. In both studies, nivolumab significantly improved response rate and overall survival compared to docetaxel. As a result, nivolumab has recently been approved by the FDA for patients with previously treated squamous cell lung cancers. NCCN has also suggested that nivolumab is reasonable therapy for patients with previously treated lung adenocarcinomas, though this has not been FDA approved yet. In this context, the recent successes of PD1/PDL1 directed therapy offer perhaps the most encouraging results for the treatment of NSCLCs in years.

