F	Nivo 3mg/kg every two weeks	52	62	5 (10%)	37 (71%)	10 (19%)	5 (10%)

[figure not shown]
Based on these data, the following schedule will be evaluated in this study:

- Nivolumab (3 mg/kg every 2 weeks, i.e. the FDA approved dose in pretreated squamous NSCLC) with the highest dose and frequency of ipilimumab feasible (1 mg/kg every 6 weeks).

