### **6.3 Subject Exclusion Criteria**

10. Patients who are pregnant or lactating.
11. Presence of activating *EGFR* mutations or *ALK* re-arrangement unless previously treated with standard TKI therapy. All patients with adenocarcinoma histology must be tested for *EGFR* and *ALK* status.
12. History of allergy to study drug components or history of severe hypersensitivity reaction of any monoclonal antibody.
13. Prior treatment with immune checkpoint inhibitor, including (but not limited to) those targeting PD-1, PD-L1, PD-L2, CTLA-4, CD137, GITR, TIM3, LAG3, or OX40
14. Any systemic anti-cancer therapy within 3 weeks prior to C1D1 of study therapy

- j. Exception is made for patients with *EGFR* or *ALK* re-arrangements who must have stopped TKI therapy at least 7 days prior to C1D1
- 15. Patients who have not previously been treated with platinum-based based doublet chemotherapy and who, in the judgment of the investigator, have rapidly progressive disease such that serious complications may arise from disease progression within the next 12 weeks will be excluded
- 16. Non-CNS radiotherapy within 1 week prior to C1D1 of study therapy
- 17. Active infection requiring therapy
- 18. Prior or current systemic immunosuppressive therapy (> 10 mg/day prednisone equivalents) within 1 week prior to C1D1 of study therapy. Inhaled, ocular, intra-articular, intranasal, and topical corticosteroids are permitted in absence of active autoimmune disease.
  - k. Adrenal replacement doses are permitted in the absence of active autoimmune disease.
- 19. Patients with known or suspected history of autoimmune disease. Subjects with type I diabetes melitis, hypothyroidism only requiring hormone replacement, resolved childhood asthma/atopy, patients with asthma requiring intermittent bronchodilator therapy, skin disorders (such as vitiligo, psoriasis, or alopecia) not requiring systemic treatment, or conditions not expected to recur in the absence of an external trigger are permitted to enroll.
- 20. Other active malignancy requiring concurrent intervention.

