Costs: Patients will be charged for physician visits, routine laboratory tests, and radiologic studies required for monitoring their condition. Pre-treatment tumor resections will be performed as standard-of-care.

The cost of research-only biopsies, nivolumab, as well as tumor tissue based- and blood based-exploratory correlatives will be covered by research funds.

Alternatives: For patients considering this trial as second-line therapy, docetaxel or erlotinib could be alternative standard options. Nivolumab would also be a standard option for patients with squamous cell lung cancer. For patients considering this trial as third-line therapy or beyond, there are no standard treatment alternatives.

Confidentiality: Every effort will be made to maintain patient confidentiality. Research and hospital records are confidential. Patients' names and any other identifying information will not be used in reports or publications resulting from this study. Other authorized agencies and appropriate internal personnel (e.g. qualified monitors from MSKCC) and external personnel (e.g. qualified monitors from BMS (the manufacturer of nivolumab and ipilimumab), its authorized agents, the FDA, and/or other governmental agencies) may review patient records as required.

Future Contact: Participants will not be routinely told of the results from research assays (e.g. DNA sequencing). With their permission, the participant and/or family members may be contacted in the future to ask if they are interested in learning about potential findings of inherited risks for cancer that may have been an outcome of the research assay testing of their samples.

Patient safety: Patients are monitored by physicians and oncology nurses who are very familiar with clinical trials. In the case of an adverse reaction, immediate medical attention is available. In the evenings and weekends, we have a 24-hour urgent care facility for outpatients. The PI or co-PI will also be available at all times to organize any necessary intervention.

Monitoring of data to ensure safety: This study is to be monitored by the institutional IRB. This incorporates an independent data and safety monitoring board established by arrangement with the National Cancer Institute. The analysis of safety will include all patients. Adverse events, including all toxic effects of treatment, will be tabulated individually, and summarized by severity and causality.

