## **18.0 INFORMED CONSENT PROCEDURES**

Before protocol-specified procedures are carried out, consenting professionals will explain full details of the protocol and study procedures as well as the risks involved to participants prior to their inclusion in the study. Participants will also be informed that they are free to withdraw from the study at any time. All participants must sign an IRB/PB-approved consent forms indicating their consent to participate.

These consent forms meet the requirements of the Code of Federal Regulations and the Institutional Review Board/Privacy Board of this Center. The consent forms will include the following:

1. The nature and objectives, potential risks and benefits of the intended study.
2. The length of study and the likely follow-up required.
3. Alternatives to the proposed study. (This will include available standard and investigational therapies. In addition, patients will be offered an option of supportive care for therapeutic studies.)
4. The name of the investigator(s) responsible for the protocol.

5. The right of the participant to accept or refuse study interventions/interactions and to withdraw from participation at any time.

This study will have two consents: one for screening prior to surgical resection of tumor tissue. This consent form will discuss that the surgical procedure will be performed as standard-of-care, but that tumor tissue will be collected for research. If sufficient tissue can be collected, the patient will be invited to participate in the main treatment part of this study and, if they agree and sign the second treatment consent, will begin screening procedures for the treatment part of this study.

Before any protocol-specific procedures can be carried out, the consenting professional will fully explain the aspects of patient privacy concerning research specific information. In addition to signing the IRB Informed Consents, all patients must agree to the Research Authorization component of the informed consent form.

Each participant and consenting professional will sign the consent form. The participant must receive a copy of the signed informed consent form.

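### Section 17.1 tells all third-line candidates that no standard alternative exists, which conflicts with Section 3 and with its own preceding sentence for checkpoint-naive squamous patients

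*Combined protocol and SAP*

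**What the plan says.** Section 3.0, under Nivolumab, reports that "nivolumab has recently been approved by the FDA for patients with previously treated squamous cell lung cancers". For the other main histology it says that "NCCN has also suggested that nivolumab is reasonable therapy for patients with previously treated lung adenocarcinomas, though this has not been FDA approved yet". Later in Section 3.0, the Study Therapy Summary justifies the nivolumab dose as "i.e. the FDA approved dose in pretreated squamous NSCLC". Neither mention of the squamous approval states a limit on the number of prior lines.

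Inclusion criterion 4 (Section 6.2) allows up to two prior lines of systemic therapy for advanced disease. Exclusion criterion 13 (Section 6.3) bars "Prior treatment with immune checkpoint inhibitor, including (but not limited to) those targeting PD-1" and several other checkpoint targets.

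The Alternatives paragraph of Section 17.1 makes three statements in this order:

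- "For patients considering this trial as second-line therapy, docetaxel or erlotinib could be alternative standard options".
- Nivolumab is also a standard option in squamous lung cancer. No line of therapy is given.
- "For patients considering this trial as third-line therapy or beyond, there are no standard treatment alternatives".

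The opening of Section 17.1 requires non-protocol options to be discussed with each patient before enrolment. Section 18.0, item 3, requires the consent forms to cover alternatives to the study: "This will include available standard and investigational therapies".

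**The concern.** The third-line sentence has no exception for histology or for earlier checkpoint exposure. Because of exclusion 13, every participant is new to nivolumab when the alternatives are discussed. A squamous patient with two prior lines is therefore previously treated and nivolumab-naive. Section 3.0 describes an approved drug for such a patient, while Section 17.1 says that no standard alternative exists.

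What is at stake is disclosure. Nivolumab is one of the two study drugs, so the omitted comparison is between nivolumab alone and nivolumab with ipilimumab plus the protocol's on-treatment biopsy. A flat statement that nothing else is available, placed in the human-subjects section, bears directly on that choice.

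**Working it through.** No statistical calculation applies. The check sets the relevant statements side by side for one type of eligible patient.

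1. **Is the patient eligible?** Take squamous histology, two prior lines and no checkpoint inhibitor. Inclusion criterion 4 admits two prior lines. Exclusion 13 makes the absence of checkpoint treatment a condition of entry. Nothing in Section 6 restricts entry by histology. The patient is eligible and would enter as third line.

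2. **What does Section 3.0 say about this patient?** Its condition for the approval is previous treatment together with squamous disease. The patient meets both, and the second mention in the Study Therapy Summary uses the same condition.

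3. **What does the third-line sentence of Section 17.1 say?** That there is no standard alternative.

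4. **Can the preceding sentence in Section 17.1 remove the conflict?** It names nivolumab as standard in squamous disease and can be read in two ways.
   - If it covers every line of therapy, the next sentence contradicts it within the same paragraph.
   - If it covers second line only, because of where it stands, Section 17.1 agrees with itself but conflicts with Section 3.0.

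   A conflict remains on either reading.

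5. **Does the same hold for adenocarcinoma?** Section 3.0 reports guideline support and says that FDA approval is lacking. Section 17.1 speaks of standard options. A treatment can be considered reasonable without being listed as standard, so both texts can be true. What remains is an omission: the guideline statement is not reflected in the second-line or the third-line sentence.

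6. **How many patients?** The firm group would number 30 × (share entering as third line) × (share of those with squamous histology). The documents give neither share and set no quota for either. They bound the count only between 0 and 30, so no useful figure can be given.

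7. **Does it reach the analysis?** The Alternatives paragraph plays no part in any endpoint, test or confidence interval in Section 14.0, or in the choice of 30 patients.

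**The case against.** The strongest reply is that Section 17.1 already names nivolumab as standard in squamous disease, immediately before the third-line sentence and without limiting it by line. On that reading the paragraph does disclose the drug, and the defect is a loosely worded next sentence. This has force: it would be too much to say that the paragraph hides nivolumab from squamous patients. It does not remove the conflict, because the third-line sentence still has no exception.

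A second reply is that the two phase 3 studies cited in Section 3.0 enrolled patients after one prior line, so their survival results do not show that nivolumab is standard in third line. That is correct as far as the evidence goes. But Section 3.0 describes the approval itself by previous treatment, with no line limit.

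A third reply is that Sections 17.1 and 18.0 already require alternatives to be discussed and put in the consent forms. Those safeguards are real, and they are also why the source paragraph should be consistent.

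A reader might go further in four ways that the documents do not support.

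- **That patients are being misinformed.** The consent forms were not available for review, and nothing says that the Section 17.1 wording is copied into them.
- **That adenocarcinoma patients meet the same contradiction.** Step 5 of the working shows that they do not.
- **That every third-line participant is affected.** Any count based on line of therapy alone ignores histology.
- **That the omission conceals a demonstrated excess of toxicity.** The table in Section 3.0 shows grade 3-4 drug-related events in 9/37 (24%) on this schedule and 10/52 (19%) on nivolumab alone. The difference is 5 percentage points, with an approximate 95% interval of -12 to +23. Median follow-up was 18 and 62 weeks, and the study was in first-line patients. The protocol itself regards the safety data as similar, and discontinuations for drug-related events were 11% and 10%. This does not establish an added risk.

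**Conclusion.** The point holds in a narrow form. The unqualified third-line sentence in Section 17.1 conflicts with Section 3.0, and on one reading with the sentence before it, for eligible checkpoint-naive squamous patients with two prior lines. For adenocarcinoma it is an omission only. The number of patients concerned cannot be derived, and no analysis or sample size changes.

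The conclusion rests on the protocol's own description of the approval, taken as written, and on the eligibility criteria as they stand. It takes no position on which treatment is standard in third line. It is worth correcting because the statement sits in the human-subjects section and concerns the alternatives that must be discussed with patients.

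**What to change.** Reconcile the Alternatives paragraph of Section 17.1 with Section 3.0 and exclusion criterion 13, setting out the alternatives by line of therapy and by histology. In doing so:

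- state which lines the squamous sentence covers, and make the third-line sentence agree with it and with Section 3.0;
- decide whether and how the guideline statement on adenocarcinoma is reflected;
- check that the alternatives text in both consent forms described in Section 18.0 matches the reconciled wording.

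Which treatments count as standard is for the protocol team to settle; the requirement is only that the sections agree. The cost is a few sentences in Section 17.1 and, if needed, matching consent wording. Accrual may slow slightly if some candidates choose treatment off study.
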